9.6. Endpoint Analyses

9.6.1. Primary Endpoint Analyses

There are two primary endpoints.

Primary analysis of MP1+2 impedances will include the ITT population evaluating mean differences at 6 months post-cochlear implantation based on a t-test at the one-sided 0.025 alpha level. If there is evidence of non-normality (based on a Shapiro-Wilks test at the 0.05 alpha level), a non-parametric alternative will be employed for the primary endpoint.

Primary analysis of speech perception performance will include the cohort of subjects randomised to CI632D and for whom CI632D is their first cochlear implant in the ITT population, evaluating the difference at 6 months post-cochlear implantation compared to baseline via a one-sample sample t-test at the one-sided 0.025 alpha level. If there is evidence of non-normality (based on a Shapiro-Wilks test at the 0.05 alpha level), a non-parametric alternative will be employed for the primary endpoint.

For both endpoints, analysis may include description of population differences in the final analysis. Additional analysis may include both the AS and PP analyses groups. Missing data will be analysed under a multiple imputation strategy that will be outlined in the Statistical Analysis Plan (SAP).

9.6.2. Secondary Endpoint Analyses

See Section 9.7 for Safety Analysis under the secondary endpoint. There are two speech perception endpoints at six months post-implantation. There are no formal statistical hypothesis planned for these endpoints; analyses will be based on descriptive statistics and nominal 95% confidence limits, with results reported separately by randomized group. The ITT population will be used for primary analysis for each endpoint. A secondary analysis will include the Per Protocol group. Missing data will be analysed under a multiple imputation strategy that will be outlined in the Statistical Analysis Plan (SAP). Analysis of estimated remaining battery life of Cl632D and Cl632 Custom Sound[®] will be conducted.

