22.	Investigator site personnel directly affiliated with this study and/or their immediate families; immediate family is defined as spouse, parent, child, or sibling.
23.	Cochlear employees or employees of Contract Research Organisations or contractors engaged by Cochlear for the purposes of this investigation.

Clinical Investigation Plan: CLTD5759

24. Currently participating, or participated within the last 30 days, in another
interventional clinical investigation/trial involving an investigational drug
or device.

Primary objectives	To show the efficacy of a dexamethasone eluting electrode in an adult population with post-lingual, bilateral, moderate to profound sensorineural hearing loss:
	 In the reduction of fibrosis (as measured by impedance) when compared to a conventional, non-dexamethasone eluting electrode.
	In the improvement of speech recognition from preoperative baseline.
Secondary objective	Demonstrate that the safety of a dexamethasone eluting electrode is similar to a standard electrode by comparison of adverse events and speech outcomes in an adult population with post-lingual, bilateral, moderate to profound sensorineural hearing loss.
Primary endpoint(s)	Difference between CI632D and CI632 mean MP1+2 impedance measurements of the available electrodes at 6 months post-cochlear implantation.
	Difference between CI632D mean speech perception performance for open-set monosyllabic word recognition in quiet in the unilateral listening condition at six months post-implant compared to preoperative baseline.
Secondary endpoint(s)	1. Comparison of CI632D and CI632 procedural and device related adverse events at 6 Months and 12 Months post-cochlear implant.
	2. Difference between CI632D and CI632 mean speech perception performance for open-set monosyllabic word recognition in quiet in the unilateral listening condition at six months post-cochlear implant.
	 Difference between CI632D and CI632 mean speech perception performance for sentence recognition in quiet in the unilateral listening condition at six months post-cochlear implant.
	4. Comparison of CI632D and CI632 Custom Sound [®] estimated remaining battery life of the sound processor at all data collection time points.
Exploratory endpoint(s)	1. Comparison of CI632D and CI632 mean change of four point impedance levels at all data collection time points.
	 Characteristics of MP1+2 impedance changes at all data collection time points and electrodes/electrode regions of CI632D and CI632.

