6.2 Secondary Objective

• Demonstrate that the safety of a dexamethasone eluting electrode is similar to a standard electrode by comparison of adverse events and speech outcomes in an adult population with post-lingual, bilateral, moderate to profound sensorineural hearing loss.

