8.5 Benefit-to Risk Rationale

Benefits of a cochlear implant to the recipient may include improved detection and recognition of environmental sounds, improved detection and recognition of conversational speech, limited ability to use the telephone and overall improvement in sound quality. The clinical safety (risks) and benefit relevant to the anticipated performance of CI600-series devices, including CI632, were evaluated in the CI600 series Clinical Evaluation Report (CER) and it was concluded that the device is effective and has a favourable safety profile. The CI600 series cochlear implants are commercially available in multiple countries. Cochlear™-sponsored clinical investigations and a systematic literature review, coupled with the design verification/validation and post-market surveillance data, established that the benefits of the CI600-series devices outweigh the risks.

The anticipated additional benefits of dexamethasone, compared with a conventional CI electrode, that will be investigated in this study are reduced fibrosis in the cochlea as measured by electrode impedances, and

improved battery life due to reduced power consumption for stimulation. The additional risks that may be posed by the dexamethasone-eluting electrode incorporated into the CI632D have been assessed and do not alter the conclusion that the potential benefits outweigh the risks for the investigational device.

It is anticipated speech outcomes for CI632D will be non-inferior to CI632.

Delivery of dexamethasone to the middle and inner ear via intratympanic or transtympanic injection, or application to the round window is widely used and accepted in cochlear implant surgery (see Section 4.2.2.1) and delivery of dexamethasone via the round window is included in the FDA-approved recommended hearing preservation surgery technique for Med-El cochlear implants

(https://www.accessdata.fda.gov/cdrh_docs/pdf/P000025S084c.pdf). Intratympanic delivery of dexamethasone has been shown to result in highly localized delivery of a relatively small quantity of drug with much lower systemic concentrations than intravenous delivery (Bird et al., 2011). Consequently, the risks of systemic side-effects are reduced. The total quantity of dexamethasone incorporated into the CI632D is approximately 15 to 110-fold smaller than the quantities used for local application in the studies referred to in Section 4.2.2.1, further reducing the risk of adverse effects.

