9. STATISTICAL CONSIDERATIONS

9.1. General Considerations

A detailed summary of statistical analysis is documented in the Statistical Analysis Plan (SAP).

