9.2.2. Secondary Endpoints

- 1. Comparison of CI632D and CI632 procedural and device related adverse events at 6 Months and 12 Months post-cochlear implant.
- 2. Difference between CI632D and CI632 mean speech perception performance for an open-set monosyllabic word recognition in quiet in the unilateral listening condition at six months post-cochlear implant.
- 3. Difference between CI632D and CI632 mean speech perception performance for sentence recognition in quiet in the unilateral listening condition at six months post-cochlear implant.
- 4. Comparison of CI632D and CI632 Custom Sound[®] estimated remaining battery life of the sound processor at all data collection time points.

Clinical Investigation Plan | Approval Date (GMT+

13.0

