9.5. Analysis Populations

Analyses of endpoints will include the following populations:

- Intent-to-Treat (ITT): all subjects that are randomised. Analysis will be based on randomisation assignment.
- As-Treated (AT): subjects that receive a CI632 or CI632D. Analysis will be based on treatment received (rather than randomisation assignment).
- Per-protocol (PP): subjects that receive a CI632 or CI632D in accordance with randomisation assignment and do not have a translocated electrode as confirmed by imaging.

In addition to these populations, there may be subgroup analysis which could include geography, sex, age or race. The complete analysis strategy will be outlined in the Statistical Analysis Plan (SAP).

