9.6.3. Exploratory Endpoint Analyses

All exploratory endpoints will be included in the final analysis for each time point. Further detail of analysis, including management of missing data, can be found in the SAP. Formal hypothesis testing is not planned for exploratory endpoints.

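### Two secondary speech endpoints are between-arm differences, but Section 9.6.2 reports each arm separately and states no estimate or interval for the difference

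*Protocol*

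**What the plan says.** Section 9.2.2 words secondary endpoint 2 as "Difference between CI632D and CI632 mean speech perception performance for an open-set monosyllabic word recognition in quiet", in the unilateral condition at six months. The Synopsis words endpoint 3 as "Difference between CI632D and CI632 mean speech perception performance for sentence recognition in quiet in the unilateral listening condition at six months post-cochlear implant". Both are contrasts between devices.

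Section 6.2 sets the secondary objective as showing similar safety, to be done "by comparison of adverse events and speech outcomes in an adult population". Section 8.5 adds an expectation: "It is anticipated speech outcomes for CI632D will be non-inferior to CI632".

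For the two speech endpoints, Section 9.6.2 plans no formal hypothesis and states that "analyses will be based on descriptive statistics and nominal 95% confidence limits, with results reported separately by randomized group". It names ITT as the main population and Per Protocol as secondary, and leaves the imputation strategy to the SAP. Section 9.3.2 confirms that the lack of formal tests with type I error control is deliberate.

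**The concern.** The endpoint is a difference between arms, while the stated analysis describes each arm on its own. Limits for two arm means are not limits for their difference, so carrying out Section 9.6.2 exactly would leave the named quantity without a reported estimate or interval.

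No other analysis stated in the protocol fills the gap. Primary endpoint 2 compares CI632D at six months with its own baseline (Section 9.6.1) and has no comparator. Section 9.6.2 is therefore the only stated analysis of 6-month unilateral speech that could show whether the eluting array does better or worse than the control. Both the secondary objective and the non-inferiority expectation refer to that comparison.

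The absence of a formal test is a declared choice and is not criticised here.

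**Working it through.** **Text against text.** The mismatch depends on no figure.

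| Place | What it states |
|---|---|
| Synopsis, 9.2.2 | Endpoints 2 and 3: difference between CI632D and CI632 at 6 months |
| 6.2 | Objective met by comparing speech outcomes |
| 9.6.1 | Primary endpoint 2: one-sample test, CI632D arm only |
| 9.6.2 | Speech endpoints: descriptive statistics and limits, by arm; only imputation left to the SAP |
| 9.6.3 | Exploratory endpoints: "Further detail of analysis, including management of missing data, can be found in the SAP" |

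Section 9.6.3 leaves analysis detail open. Section 9.6.2 does not: it fixes a reporting form.

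**Plan's own figure.** The protocol gives no precision or sample size for the speech contrast. Its only two-arm calculation is for impedance: 1.5 kOhm, SD 2.0, one-sided 0.025, power 0.9, 39 per arm. The noncentral t gives power 0.897 at 38 and 0.905 at 39 per arm, so 39 is reproduced. The present point does not touch it.

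**How wide the missing interval would be (illustration).**

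Inputs:
- SD 22.6 points, the SD of change in CNC words in a predicate-device study (Section 9.4). Using it as the SD of the 6-month score in both arms is an assumption; 18 to 28 is an assumed range.
- Up to 60 per arm (Section 7.1); 54 per arm after 10% attrition (60 × 0.9).
- Looks at 50, 80, 100 and 120 randomised (Section 9.8), i.e. 25, 40, 50 and 60 per arm. Secondary analysis may follow any look at which both primary nulls are rejected.

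Half-width of the 95% CI for the unadjusted difference = t(0.975, 2n−2) × SD × √(2/n).

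At n = 60 and SD 22.6: 1.980 × 22.6 × √(2/60) = 1.980 × 4.126 = 8.17.

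| n per arm | SD 18 | SD 22.6 | SD 28 |
|---|---|---|---|
| 60 | 6.5 | 8.2 | 10.1 |
| 54 | 6.9 | 8.6 | 10.7 |
| 50 | 7.1 | 9.0 | 11.1 |
| 40 | 8.0 | 10.1 | 12.5 |
| 25 | 10.2 | 12.9 | 15.9 |

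These widths ignore the extra uncertainty from imputation. Sentence scores cannot be done the same way, because the protocol gives no SD for them.

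**Why by-arm limits do not stand in.** At n = 60 and SD 22.6, each arm mean has half-width t(0.975, 59) × 22.6/√60 = 5.84. The two arm intervals stop overlapping only at a difference of 2 × 5.84 = 11.7 points, which is 11.68/8.17 = 1.43 times the half-width of the interval for the difference. By the normal approximation, non-overlap corresponds to z = 1.96 × √2 = 2.77, a two-sided level of about 0.006. An observed difference between about 8.2 and 11.7 points would leave the arm intervals overlapping while the interval for the difference excludes zero.

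**With baseline adjustment.** The residual variance given baseline is the minimum over b of Var(Y − bB), so it cannot exceed Var(Y − B), the variance of change. No correlation need be assumed. The expected half-width is then at most about t(0.975, 2n−3) × 22.6 × √(2/n) × √(1 + 1/(2n−4)), where the last factor allows for chance baseline imbalance: 8.2 at n = 60, 8.7 at n = 54 and 13.0 at n = 25. In a simulation with an assumed baseline SD of 12 and correlation 0.3, the mean adjusted half-width was 7.95 at n = 60 and 12.58 at n = 25, so under those assumptions the gain from adjustment is small.

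**The case against.** The strongest reply is that tabulating a descriptive secondary endpoint is SAP business. Sections 9.1 and 9.5 place the detailed analysis and complete strategy there, and nothing in 9.6.2 forbids reporting a difference. Section 9.2.2 already names the quantity, so the by-arm phrase can be read as a display rule added to it. Section 6.2 asks only for a comparison, which side-by-side summaries can partly serve. Section 8.5 is an expectation with no margin or analysis attached. A reader can subtract the means and approximate an interval.

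Much of this stands. The SAP may already contain the estimate, nothing is concealed, and the consequence is moderate. The contrast with adverse events should not be pressed: Section 9.7 says rates will be compared between arms but gives no estimate or interval either. The overlap calculation matters only if someone judges by overlap, which the protocol does not plan.

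What does not stand is that this is mere silence. Section 9.6.2 states the reporting form for these endpoints and defers only imputation. The by-arm reading is the natural one, and an SAP written faithfully to it would repeat the omission.

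**Conclusion.** The point holds. The analysis stated in Section 9.6.2 does not deliver secondary endpoints 2 and 3 as the Synopsis and Section 9.2.2 define them. It should be corrected, but it does not threaten the trial: both primary analyses and the sample size are untouched.

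The conclusion rests on the text alone. The widths (about ±8 points at full size and ±13 at the first look) rest on the borrowed SD of 22.6 and show only what a reader would learn from the interval. The SAP was not available; if it already specifies the between-arm difference with its interval, what remains is to align the protocol wording.

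**What to change.** In Section 9.6.2 keep the arm summaries and add a sentence to this effect: the CI632D-minus-CI632 difference in 6-month unilateral CNC word and AzBio sentence scores will be reported with a nominal two-sided 95% confidence interval, adjusted for the preoperative score of the implanted ear, in the populations and under the imputation already stated. No test, margin or alpha is added, which keeps to Section 9.3.2. An unadjusted difference with its interval would also cure the omission. Adjustment is a refinement that needs no new data, because Section 7.3.2.3 already collects each ear's preoperative score on both tests.

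While editing, correct Section 9.3.2, which describes the speech endpoints as changes where Section 9.2.2 has 6-month scores, and counts three secondary endpoints where 9.2.2 lists four. This is clerical.

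The cost is one model per endpoint and a few words. Under Section 18 a protocol change is an amendment with ethics committee notification, so it is best carried with the next one; meanwhile the SAP can specify the estimate, since 9.6.2 does not bar it. The sponsor should expect that the interval may not exclude a modest deficit, especially after an early look.

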9.6.3. Exploratory Endpoint Analyses

All exploratory endpoints will be included in the final analysis for each time point. Further detail of analysis, including management of missing data, can be found in the SAP. Formal hypothesis testing is not planned for exploratory endpoints.

9.7. Safety Analyses

Safety analysis will be completed with the AT population at both 6 months and 12 months post-cochlear implantation. The rate of AE type will be compared between treatment and control arm.

For AE/ADEs and DDs, data will be tabled to present event type, severity, device/procedural relationship, count and percentage, and subjects with event will be summarised by randomisation group. Any subjects who died, who discontinued an intervention due to an AE/ADEs, or who experienced a severe or an SAE/SADEs will be summarised separately. In addition to Secondary Endpoint Analyses, AE/ADE and DD frequency data will be provided to the IDMC in accordance to the IDMC Charter.

9.8. Interim Analyses

Group sequential analysis based on an O'Brien-Fleming like alpha spending function, will be completed for the primary endpoints following the collection of 6 Month data for subjects at the following intervals: the first 50 randomised subjects, first 80 randomised subjects, first 100 randomised subjects, and first 120 randomised subjects. If the null hypothesis cannot be rejected for both primary endpoints following analysis at each interval (stopping criteria), then further analysis will take place at the subsequent interval until the final analysis of the 120 randomised subjects.

The first primary endpoint will be analysed first. The second primary endpoint will be analysed if the null hypothesis is rejected. Analysis of secondary or exploratory endpoints will not occur until both the primary endpoint null hypotheses are rejected, or 120 randomised subjects are analysed.

Prior to final analysis at study completion, group sequential analysis may be used as part of Premarket Approval (PMA) if both primary endpoint null hypotheses are rejected.

9.9. Sub-Group Analyses

Sub-group analyses may be completed as an additional analysis to any endpoint. Sub-groups may include analysis of specific clinical investigation sites, sex, age, race or specific procedural/device outcome (such as translocation). Detail of sub-group analysis can be found in the SAP.

10. INFORMED CONSENT PROCESS

The Investigator shall obtain written informed consent from the subject using an approved ICF prior to any clinical investigation-related examination or activity. The rationale of the clinical investigation, as well as the benefits and risks, what participation will involve, and established alternatives to participation will be explained to the subject in native non-technical language, understandable to the subject. Ample time will be provided for the subject to enquire about details of the clinical investigation and to decide whether to participate.

All questions about the clinical investigation shall be answered to the satisfaction of the subject or the subject's legally acceptable representative. Subjects shall not be coerced or unduly influenced to participate or to continue to participate in a clinical investigation. They shall not waive or appear to waive their legal rights.

Each subject (or their legally designated representative) and the person who conducted the informed consent discussion, shall sign and personally date the Informed Consent Form (ICF). Where required, an independent and impartial witness shall sign and personally date the ICF. A copy of the signed ICF shall be given to the subject. The original signed ICF shall be archived in the Investigator's Site File or subject file at the investigational site.

This process shall be documented in the subject's source documents.

The subject, or the subject's legally designated representative, shall be informed in a timely manner if new information becomes available that may be relevant to the subject's willingness to continue participation in the clinical investigation. The communication of this information must be documented as an update to the ICF and re-consent of the subject.

11. ADVERSE EVENTS AND DEVICE DEFICIENCIES

11.1. Definitions

11.1.1. Adverse Event

An adverse event (AE) is any untoward medical occurrence, unintended disease or injury, or untoward clinical signs (including abnormal laboratory findings) in subjects, users or other persons whether or not related to the investigational medical device and whether anticipated or unanticipated.

NOTE 1: This definition includes events related to the investigational medical device or the comparator.

NOTE 2: This definition includes events related to the procedures involved.

NOTE 3: For users and other persons, this definition is restricted to events related to the use of investigational medical devices or comparators.

11.1.2. Adverse Device Effect

An adverse device effect (ADE) is an AE related to the use of an investigational medical device.

NOTE 1: This includes any AE resulting from insufficient or inadequate instructions for use, deployment, implantation, installation or operation, or any malfunction of the investigational medical device.

NOTE 2: This definition includes any event resulting from use error or from intentional misuse of the investigational medical device.

NOTE 3: This includes 'comparator' if the comparator is a medical device.

11.1.3. Serious Adverse Event

A serious adverse event (SAE) is any AE that led to any of the following:

- 1) death,
- 2) serious deterioration in the health of the subject, users, or other persons as defined by one or more of the following:
- a life-threatening illness or injury, or
- a permanent impairment of a body structure or a body function including chronic diseases, or
- in-patient or prolonged hospitalisation, or
- medical or surgical intervention to prevent life-threatening illness or injury or permanent impairment to a body structure or a body function,
- 3) foetal distress, foetal death or a congenital abnormality, or birth defect including physical or mental impairment.

NOTE: Planned hospitalisation for a pre-existing condition, or a procedure required by the CIP, without serious deterioration in health, is not considered a SAE.

